11.7 Pregnancy in the Clinical Study

Women who are pregnant or lactating (as stated by subject) at the time of study entry are excluded from participation. However, pregnancy should be included in the Pregnancy eCRF if a woman becomes pregnant (as stated by the subject) during the study. Subjects who become pregnant during the study will not be discontinued; however data will be excluded

from the effectiveness analyses because pregnancy can alter refraction and visual acuity results.

Pregnancy is not reportable as an AE; however, complications may be reportable and will be decided on a case-by-case basis.

12 ANALYSIS PLAN

Continuous variables will be summarized using the number of observations, mean, SD, median, minimum, and maximum, as well as CIs or confidence limits where applicable. Categorical variables will be summarized with frequencies and percentages from each category.

Any deviations to the analysis plan will be updated during the course of the study as part of a protocol amendment or will be detailed in the clinical study report.

[REDACTED]

12.1 Subject Evaluability

Final subject evaluability must be determined prior to breaking the code for masked treatment (lens sequence) assignment and locking the database, based upon the data evaluability plan (DEP).

12.2 Analysis Sets

12.2.1 Safety Analysis Set

Safety analyses will be conducted using the safety analysis set on a treatment-emergent basis. As such, the safety analysis set will include all subjects/eyes exposed to any study lens evaluated in this study. [REDACTED]

[REDACTED], any AE or device deficiency occurring after informed consent and prior to the initial exposure to the study lenses (test or comparator) under evaluation in this clinical protocol will be listed as pretreatment.

For treatment-emergent safety analyses, subjects/eyes will be categorized under the actual study lenses exposed in the corresponding study lens sequence.

12.2.2 Full Analysis Set

The full analysis set (FAS) is the set of all randomized subjects who are exposed to any study lenses evaluated in this study; [REDACTED]

12.2.3 Per Protocol Analysis Set

The per protocol (PP) analysis set is a subset of FAS and excludes all data/subjects that have met any of the critical deviation or evaluability criteria identified in the DEP.

12.3 Demographic and Baseline Characteristics

Demographic information will be summarized by lens sequence and overall. Frequencies and percentages will be presented for categorical variables such as sex, age group, race, and ethnicity. Number of observations, mean, SD, median, minimum, and maximum will be presented for continuous variables such as age.

12.4 Effectiveness Analyses

This study defines 1 primary effectiveness endpoint; [REDACTED]

[REDACTED]

[REDACTED] the FAS as the primary analysis set. [REDACTED]

[REDACTED]

[REDACTED]

[REDACTED]

[REDACTED]

[REDACTED]

[REDACTED]

12.4.1 Analysis of Primary Effectiveness Endpoint(s)

The primary objective of this study is to evaluate the binocular VA at distance of LID233309 lenses and Oasys MF contact lenses at Week 1.

[figure not shown]
The primary endpoint is binocular HC/HI distance (4 m) VA with study lenses at Week 1, collected for each eye, on the logMAR scale.

[figure not shown]
12.4.1.1 Statistical Hypotheses

No inferences are to be made on the primary effectiveness endpoint; therefore, no hypotheses are formulated.

12.4.1.2 Analysis Methods

At Week 1, descriptive statistics will be provided as number of observations, mean, SD, median, minimum, and maximum, along with a two-sided 95% confidence interval. Similarly, for Dispense and Week 2.

12.5 Handling of Missing Data

All data obtained in evaluable subjects/eyes will be included in the analysis. No imputation for missing values will be carried out for the primary and key exploratory effectiveness analyses.

12.6 Safety Analyses

The safety endpoints are:

- AEs
- Biomicroscopy findings
- Device deficiencies

There are no safety hypotheses planned in this study. The focus of the safety analysis will be a comprehensive descriptive assessment of occurrence of AEs as well as the other listed parameters.

All AEs occurring from the time a subject signs informed consent to study exit will be accounted for in the reporting. Safety analyses will be conducted using the safety analysis set on a treatment-emergent basis. Descriptive summaries (frequencies and percentages) for ocular and nonocular AEs will be presented by Medical Dictionary for Regulatory Activities Preferred Terms. AEs leading to study discontinuation, significant nonserious AEs, and SAEs will be identified. Individual subject listings will be provided, as necessary.

Separate individual subject listings will be provided for AEs that occur after signing informed consent but prior to exposure to study lenses, and for AEs that occur during the washout periods.

Each biomicroscopy parameter will be tabulated by its grade. For each biomicroscopy parameter, counts and percentages of eyes that experience an increase of ≥ 2 grades from baseline (last assessment prior to study lens) to any subsequent visit within the same period will be presented. A supportive listing will be generated which will include all biomicroscopy data from all visits within the same period for those eyes experiencing the increase.

Two listings (prior to exposure to study lenses and treatment-emergent) of device deficiencies will be provided. Additionally, each device deficiency category will be tabulated.

No inferential testing will be conducted for the safety analyses.

12.7 Interim Analyses and Reporting

There are no plans to conduct an interim analysis and no criteria by which the study would be terminated early based upon statistical determination.

12.8 Sample Size Justification

Although inferential testing is not planned for the primary and effectiveness endpoints, expected precision of the observed results is provided for the chosen sample size of 92, [REDACTED]

Visual Acuity

With the assumed standard deviation of 0.12, a two-sided 95% CI for the mean of distance visual acuity based on t-statistics, coverage probability of 0.85 will extend 0.027 (~1 Snellen letter) from the observed mean.

13 DATA HANDLING AND ADMINISTRATIVE REQUIREMENTS

13.1 Subject Confidentiality

The investigator must ensure that the subject's identity is kept confidential throughout the course of the study. In particular, the investigator must keep an enrollment log with confidential identifying information that corresponds to the subject numbers and initials of each study participant. The study sponsor may collect a copy of the enrollment log *without any directly identifying subject information*.

The study sponsor may share patient-level data collected in this trial with qualified researchers to help facilitate product development or enhancements in research that is not directly related to the study objectives. The informed consent explains this to the study subject.

13.2 Completion of Source Documents and Case Report Forms

The nature and location of all source documents will be identified to ensure that original data required to complete the CRFs exist and are accessible for verification by the site monitor,

and all discrepancies shall be appropriately documented via the query resolution process. Site monitors are appointed by the study sponsor and are independent of study site staff.

If electronic records are maintained, the method of verification must be determined in advance of starting the study.

At a minimum, source documents include the following information for each subject:

- Subject identification (name, sex, race/ethnicity)
- Documentation of subject eligibility
- Date of informed consent
- Dates of visits
- Documentation that protocol specific procedures were performed
- Results of study parameters, as required by the protocol
- IP accountability records
- Documentation of AEs and other safety parameters (if applicable)
- Records regarding medical histories and the use of concomitant therapies prior to and during the study
- Date of study completion and reason for early discontinuation, if applicable

It is required that the author of an entry in the source documents be identifiable. Direct access to source documentation (medical records) must be allowed for the purpose of verifying that the data recorded on the CRF are consistent with the original source data.

Only designated individuals at the site will complete the CRFs. The CRFs must be completed at regular intervals following the clinical study visit schedule. It is expected that all data reported have corresponding entries in the source documents. The principal investigator is responsible for reviewing and certifying that the CRFs are accurate and complete. The only subject identifiers recorded on the CRFs will be subject number, and subject demographic information.

13.3 Data Review and Clarifications

A review of CRF data to the subject's source data will be completed by the site monitor to ensure completeness and accuracy. After the CRFs have been completed, additional data clarifications and/or additions may be needed as a result of the data cleaning process. Data clarifications are documented and are part of each subject's CRF.

13.4 Sponsor and Monitoring Responsibilities

The study sponsor will select principal investigators who are qualified by education, training, and experience to assume responsibility for the proper conduct of this clinical trial. For this study, the principal investigator and subinvestigators must be eye care professionals appropriately licensed to diagnose and treat subjects with the condition under study.

The study sponsor is financially funding this clinical trial and will compensate the investigator and/or the institution(s) at which the study is conducted in accordance with a signed clinical trial agreement.

The study sponsor will designate a monitor to conduct the appropriate site visits at the appropriate intervals according to the study monitoring plan. The clinical investigation will be monitored to ensure that the rights and well-being of the subjects are protected, the reported data are accurate, complete, and verifiable from the source documents, and the study is conducted in compliance with the current approved protocol (and amendments[s], if applicable), with current GCP, and with applicable regulatory requirements.

The site may not screen subjects or perform the informed consent process on any subject until it receives a notification from an appropriate study sponsor representative that the site may commence conducting study activities. Monitoring will be conducted periodically while the clinical study is ongoing. Monitoring methods may include site visits, telephone, written and fax correspondence. Close-out visits will take place after the last visit of the last subject at the site.

A coordinating investigator may be identified by the study sponsor to review and endorse the final study report. In cases where a coordinating investigator is engaged, the study sponsor will select the coordinating investigator based upon their experience, qualifications, active study participation, and their willingness and availability to take on this role.

13.5 Regulatory Documentation and Records Retention

The investigator is required to maintain up-to-date, complete regulatory documentation as indicated by the study sponsor and the investigator's files will be reviewed as part of the ongoing study monitoring. Financial information is to be kept separately.

Additionally, the investigator must keep study records and source documents consistent with the terms of the clinical study agreement with the study sponsor. If the investigator retires, relocates, or for any other reason withdraws from responsibility of keeping the study records, then the study sponsor must be notified, and suitable arrangements made for retention of

study records and source documents needed to comply with national and international regulations.

13.6 Quality Assurance and Quality Control

The study sponsor will secure agreement from all involved parties to ensure direct access to all study related sites, source data and documents, and reports for the purpose of monitoring and auditing by the study sponsor, and inspection by domestic and foreign regulatory authorities. Quality control will be applied to each stage of data handling to ensure that all data are reliable and have been processed correctly. Agreements made by the study sponsor with the investigator/institution and any other parties involved in the clinical study will be provided in writing as part of the protocol or as a separate agreement.

14 ETHICS

Investigations are conducted in compliance with Good Clinical Practices; international and national regulations, laws and guidelines; EN ISO 14155; the conditions of approval imposed by reviewing IRBs/IECs or regulatory authorities; and in accordance with the ethical medical research principles outlined in the Declaration of Helsinki.

- The SOPs of the study sponsor and contract research organizations participating in the conduct of the clinical study and all other applicable regulations shall apply.
- Notifications and timelines for reporting protocol deviations should be based upon applicable Ethics Committee requirements.

The investigator must ensure that all personnel involved in the conduct of the study are qualified to perform their assigned responsibilities through relevant education, training, and experience. The investigator and all clinical study staff must conduct the clinical study in compliance with the protocol. The investigator is not allowed to deviate from the protocol except to protect the rights, safety, and well-being of human subjects under emergency circumstances. Emergency deviations may proceed without prior approval of the sponsor and the IRB/EC, but shall be documented and reported to the sponsor and the IRB/EC as soon as possible. Deviations from this protocol, regulatory requirements, and/or GCP must be recorded and reported to the sponsor prior to database lock. If needed, corrective and preventive action should be identified, implemented, and documented within the study records. Failure to implement identified corrective and preventative actions may result in site closure by the sponsor. Use of waivers to deviate from the clinical protocol is prohibited.

Before clinical study initiation, this protocol, the informed consent form, any other written information given to subjects, and any advertisements planned for subject recruitment must

be approved by an IRB/IEC. The investigator must provide documentation of the IRB/IEC approval to the study sponsor. The approval must be dated and must identify the applicable protocol, amendments (if any), informed consent form, assent form (if any), all applicable recruiting materials, written information for subject, and subject compensation programs. The IRB/IEC must be provided with a copy of the IB, any periodic safety updates, and all other information as required by local regulation and/or the IRB/IEC. Any additional requirements imposed by the EC or regulatory authority shall be followed. At the end of the study, the investigator must notify the IRB/IEC about the study's completion. The IRB/IEC also must be notified if the study is terminated prematurely. Finally, the investigator must report to the IRB/IEC on the progress of the study at intervals stipulated by the IRB/IEC.

Voluntary informed consent must be obtained in writing from every subject. The obtaining of consent shall be documented before any procedure specific to the clinical investigation is applied to the subject.

The investigator must have a defined process for obtaining the required consent. Specifically, the investigator, or their delegate, must explain the clinical study to each potential subject and the subject must indicate voluntary consent by signing and dating the approved informed consent form. The subject must be provided an opportunity to ask questions of the investigator, and if required by local regulation, other qualified personnel. The investigator must provide the subject with a copy of the consent form written in a language the subject understands. The consent document must meet all applicable local laws and provide subjects with information regarding the purpose, procedures, requirements, and restrictions of the study, along with any known risks and potential benefits associated with the IP and the study, the available compensation, and the established provisions for maintaining confidentiality of personal, protected health information. Subjects will be told about the voluntary nature of participation in the study and must be provided with contact information for the appropriate individuals should questions or concerns arise during the study. The subject also must be told that their records may be accessed by appropriate authorities and sponsor-designated personnel. The investigator must keep the original, signed copy of the consent (file in subject's medical records) and must provide a duplicate copy to each subject according to local regulations.

The investigator must have a defined process in case a subject would like to withdraw their consent(s). The investigator is the designated contact point for any such withdrawals.

The investigator must have a defined process in case a subject would like to exercise any of their rights under applicable Data Protection laws. The investigator is the designated contact point for any such requests.

The study sponsor assures that the key designs of this protocol will be registered on public databases where required by current regulations, and, as applicable, results will be posted.

15 REFERENCES

[figure not shown]

1 STUDY OBJECTIVES AND DESIGN

1.1 Study Objectives

PRIMARY OBJECTIVE

The primary objective of this study is to evaluate binocular VA at distance of LID233309 lenses and Oasys MF lenses.

10. *Journal of the American Statistical Association*, 1980, 75, 338-342.

SAFETY OBJECTIVE

The safety objective is to describe the safety profile of the study products.

1.2 Study Description

Key components of the study are summarized in Table 1-1.

Table 1-1 **Study Description Summary**

[figure not shown]
	
Target to complete: 92
 
Planned to enroll: ~96

Number of Sites	~8 US
Test Product	Alcon serafilcon A Multifocal contact lenses (serafilcon A; LID233309)
Comparator Product	ACUVUE® OASYS MULTIFOCAL with PUPIL OPTIMIZED DESIGN contact lenses (Oasys MF; senofilcon A)
Planned Duration of Exposure	~28 days total duration (test and comparator): Test Product: 14 days Comparator Product: 14 days
Visits	
Prescreening (optional)
 
Visit 1: Screening/Baseline/Lens Fitting
 
Visit 2: Dispense Lens 1 [2 (at least 48 hours) - 4 days after the end of Visit 1*]
 
Visit 3: Week 1 Follow-up Lens 1 [7 -0/+1 days after Visit 2]
 
Visit 4: Week 2 Follow-up Lens 1 [7 -0/+1 days after Visit 3]
 
Visit 5: Dispense Lens 2 [2 (at least 48 hours) - 4 days after the end of Visit 4*]
 
Visit 6: Week 1 Follow-up Lens 2 [7 -0/+1 days after Visit 5]
 
Visit 7: Week 2 Follow-up Lens 2/Exit [7 -0/+1 days after Visit 6]
 
* Washout period with habitual spectacles only after Visit 1 and after Visit 4

A study design schematic is depicted in Figure 1-1.

Figure 1-1

Study Design

[figure not shown]
Study Design
Prospective, Randomized, Double-masked, Cross-over Dispensing Trial

1.3 Randomization

[figure not shown]
A member of the Randomization Programming group at Alcon who is not part of the study team will generate the randomized allocation schedule(s) for lens sequence assignment.

Randomization will be implemented in the Electronic Data Capture (EDC)/randomization integration system.

1.4 Masking

This study is double-masked (study lenses).

1.5 Interim Analysis

There are no plans to conduct an interim analysis and no criteria by which the study would be terminated early based upon statistical determination.

2 ANALYSIS SETS

2.1 Safety Analysis Set

Safety analyses will be conducted using the safety analysis set on a treatment-emergent basis. As such, the safety analysis set will include all subjects/eyes exposed to any study lenses evaluated in this study. [REDACTED]

[REDACTED], any adverse event (AE) or device deficiency occurring after informed consent and prior to the initial exposure to the study lenses (test or comparator) under evaluation in this clinical protocol will be listed as pretreatment.

For treatment-emergent safety analyses, subjects/eyes will be categorized under the actual study lenses exposed in the corresponding study lens sequence.

Adverse events occurring from the time of informed consent but prior to first exposure to study lenses will be summarized in subject listings.

2.2 Full Analysis Set

The full analysis set (FAS) is the set of all randomized subjects who are exposed to any study lenses evaluated in this study. [REDACTED]

2.3 Per Protocol Analysis Set

The per protocol (PP) analysis set is a subset of FAS and excludes all data/subjects that have met any of the critical deviation or evaluability criteria identified in the Data Evaluability Plan (DEP).

3 SUBJECT CHARACTERISTICS AND STUDY CONDUCT SUMMARIES

[REDACTED]

[REDACTED]

[REDACTED]

[REDACTED]

[REDACTED]

The following tables will be presented:

- Subject Disposition by Lens Sequence
- Subject Disposition by Study Lens Sequence
- Analysis Sets by Study Lens
- Analysis Sets by Study Lens Sequence
- Subject Accounting by Lens
- Subject Accounting by Study Lens Sequence
- Demographics by Lens Sequence
- Demographics by Study Lens Sequence
- Baseline Characteristics by Study Lens Sequence [lens brand; hours of digital device use per day; pupil size]

Subject accounting and demographics tables will be summarized on the safety, full, and per protocol analysis datasets. Baseline characteristics will be summarized on the full and per protocol analysis datasets.

In addition, the following subject listings will be provided:

- Listing of Subjects Excluded from Protocol Defined Analysis Sets
- Listing of Lens Sequence Assignment by Investigator
- Listing of Subjects Discontinued from Study

4 EFFECTIVENESS ANALYSIS STRATEGY

This study defines 1 primary effectiveness endpoint, [REDACTED]

[REDACTED]
effectiveness evaluations will use the FAS as the primary analysis set. [REDACTED]

[REDACTED]

[REDACTED]

[REDACTED]

[REDACTED]

[REDACTED]

[REDACTED]

Continuous variables will be summarized using the number of observations, mean, standard deviation (SD), median, minimum, and maximum, as well as confidence intervals/limits as applicable. Categorical variables will be summarized with frequencies and percentages from each category.

All data obtained in evaluable subjects/eyes will be included in the analysis. No imputation for missing values will be carried out for the primary and key exploratory effectiveness analyses.

A listing of select effectiveness data will also be provided.

4.1 Effectiveness Endpoints

Primary Effectiveness Endpoint

The primary endpoint is binocular High Contrast/High Illumination (HC/HI) distance (4 m) VA with study lenses at Week 1, collected on the logMAR scale.

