9 TREATMENTS ADMINISTERED

9.1 Investigational Product(s)

Test Product(s): LID233309

Comparator Product(s) (If applicable): Oasys MF

Table 9–1 Test Product

Test Product	Serafilcon A Multifocal contact lenses (LID233309)
Manufacturer	Alcon Laboratories, Inc. [name] USA
Indication for use and intended purpose in the current study	The investigational frequent replacement multifocal contact lens is indicated for the optical correction of presbyopia with or without refractive ametropia (myopia and hyperopia) persons with nondiseased eyes. The lenses are intended for daily wear (less than 24 hours while awake), with removal for cleaning and disinfection (chemical, not heat) prior to reinsertion.
Product description and parameters available for this study	
 • Material: Serafilcon A • Water content: 55% 
Power range: Limited lens parameters will be available for use in this study:
 
 ○ -0.50 D to -4.00 D in 0.25 D steps, -5.00 D, -6.00 D, and -8.00 D with ADD of LO, MED, or HI (as available) ○ +1.00 D to +3.00 D in 0.25 D steps, +5.00 D and +6.00 D with ADD of LO, MED, or HI (as available) 
 • Base curve (mm): 8.4 (Target) • Diameter (mm): 14.2 (Target)
Formulation	Refer to IB
Usage	
 • Wear: 
 ○ Daily Wear

	
 ○ Bilateral ● Replacement period: 
 ○ Replaced weekly for ~14 days ○ The unmasked staff must maintain the subject and investigator masking to the study product being used. ● Exposure: Study lenses are to be worn during typical contact lens wearing hours, on all days during the study lens wearing period, at least 10 hours per day, over each wear cycle (7 days [-0/+1] according to randomization assignment). Subjects will be asked to wear their study lenses for 16 hours on the days prior to each Follow-up Visit (Visit 3, 4, 6, & 7). ● Lens Care: Cleaned and disinfected with CLEAR CARE Cleaning & Disinfecting Solution after each use ● Replacement lenses will not be provided to the subject. In the event a lens needs to be replaced, the subject must return to the site for a replacement lens. Until the replacement lens is obtained, the subject must store the study lenses as instructed. Refer to MOP for detailed instructions.

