Product description and parameters available for this study	
Commercial description for Product:
 
• Material: Senofilcon A• Water content: 38%• Base curve (mm): 8.4 mm• Diameter (mm): 14.3 mm 
Power range: Limited lens parameters will be available for use in this study:
 
○ -0.50 D to -4.25 D in 0.25 D steps, -5.25 D, -6.25 D, and -8.25 D with ADD of LO, MID, or HI (as available)○ +0.75 D to +3.00 D in 0.25 D steps, +4.75 D and +5.75 D with ADD of LO, MID, or HI (as available)
Formulation	Refer to package insert
Usage	
• Wear:
○ Daily wear○ Bilateral• Replacement period:
○ Replaced biweekly for ~14 days○ The unmasked staff must maintain the subject and investigator masking to the study product being used• Exposure: Study lenses are to be worn during typical contact lens wearing hours, on all days during the study lens wearing period, at least 10 hours per day, over the wear cycle (total ~14 days of 7 days [-0/+1] in each follow-up, according to randomization assignment). Subjects will be asked to wear their study lenses for 16 hours on the days prior to each Follow-up Visit (Visit 3, 4, 6, & 7).• Lens Care: Cleaned and disinfected with CLEAR CARE Cleaning & Disinfecting Solution after each use• Replacement lenses will not be provided to the subject. In the event a lens needs to be replaced, the subject must return to the site for a replacement lens. Until the replacement lens is obtained, the subject must store the study lenses as instructed. Refer to MOP for detailed instructions.
Number/Amount of Product to be	Subjects will receive 1 pair of comparator lenses as per randomization, in parameters as determined during trial.

Provided to the subject	
Packaging description	Provided in Commercial Packaging
Labeling description	Commercial foil
Training and/or experience requirements for device	No additional training or experience is required to administer the comparator.
Storage conditions	Lenses are to be stored at room temperature
Additional identifying information	N/A

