4.3 Statistical Methods for Effectiveness Analyses

Primary Effectiveness

At Week 1, descriptive statistics will be provided as number of observations, mean, SD, median, minimum, and maximum, along with a two-sided 95% confidence interval.

Similarly, for Dispense and Week 2.

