7 SAMPLE SIZE AND POWER CALCULATIONS

Although inferential testing is not planned for the primary and effectiveness endpoints, expected precision of the observed results is provided for the chosen sample size of 92. [REDACTED]

Visual Acuity

With the assumed SD of 0.12, a two-sided 95% CI for the mean of distance visual acuity based on t-statistics, coverage probability of 0.85 will extend 0.027 (~1 Snellen letter) from the observed mean.

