		Fitting Lens 1 (Fit Period 1) and Fitting Lens 2 (Fit Period 2)	Lens 1 (Period 1)			Lens 2 (Period 2)			Early Exit	Unscheduled Visit
			Visit 1 Screening/ Baseline/ Lens Fitting	Visit 2 Dispense Lens 1	Visit 3 Week 1 Follow-up Lens 1	Visit 4 Week 2 Follow-up Lens 1	Visit 5 Dispense Lens 2	Visit 6 Week 1 Follow-up Lens 2	Visit 7 Week 2 Follow-up Lens 2/Exit	
Procedure/ Assessment	Pre-screening		Day 1 [Visit 2 must occur after washout with habitual spectacles, 2 (at least 48 hours) - 4 days after the end of Visit 1]	(7 -0/+1 days after Visit 2)	(7 -0/+1 days after Visit 3)	Day 1 [Visit 5 must occur after washout with habitual spectacles, 2 (at least 48 hours) - 4 days after the end of Visit 4]	(7 -0/+1 days after Visit 5)	(7 -0/+1 days after Visit 6)		
Determine and record study lens power to be dispensed		X								
Dispense study lenses*			X	X		X	X			(X)
			X	X (Old & New)	X	X	X (Old & New)	X	(X)	(X)

		Fitting Lens 1 (Fit Period 1) and Fitting Lens 2 (Fit Period 2)	Lens 1 (Period 1)			Lens 2 (Period 2)			Early Exit	Unscheduled Visit
			Visit 1 Screening/ Baseline/ Lens Fitting	Visit 2 Dispense Lens 1	Visit 3 Week 1 Follow-up Lens 1	Visit 4 Week 2 Follow-up Lens 1	Visit 5 Dispense Lens 2	Visit 6 Week 1 Follow-up Lens 2	Visit 7 Week 2 Follow-up Lens 2/Exit	
Procedure/ Assessment	Pre-screening		Day 1 [Visit 2 must occur after washout with habitual spectacles, 2 (at least 48 hours) - 4 days after the end of Visit 1]	(7 -0/+1 days after Visit 2)	(7 -0/+1 days after Visit 3)	Day 1 [Visit 5 must occur after washout with habitual spectacles, 2 (at least 48 hours) - 4 days after the end of Visit 4]	(7 -0/+1 days after Visit 5)	(7 -0/+1 days after Visit 6)		
				X	X (Old & New)	X	X	X (Old & New)	X	(X)
VA (logMAR) with study lenses at			X	X (Old & New)	X	X	X (Old & New)	X	(X)	(X)
• Distance (4 m; OD, OS, OU)										

		Fitting Lens 1 (Fit Period 1) and Fitting Lens 2 (Fit Period 2)	Lens 1 (Period 1)			Lens 2 (Period 2)			Early Exit	Unscheduled Visit
			Visit 1 Screening/ Baseline/ Lens Fitting	Visit 2 Dispense Lens 1	Visit 3 Week 1 Follow-up Lens 1	Visit 4 Week 2 Follow- up Lens 1	Visit 5 Dispense Lens 2	Visit 6 Week 1 Follow- up Lens 2	Visit 7 Week 2 Follow- up Lens 2/Exit	

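### Does the plan leave open which of two Week 1 distance acuity readings is the primary value?

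*SAP*

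**What the plan says.** **Endpoint.** SAP 4.1 defines the primary endpoint as binocular high-contrast, high-illumination distance (4 m) "VA with study lenses at Week 1, collected on the logMAR scale". Protocol Table 6-1 also says binocular, at Week 1. Protocol 12.4.1 says binocular too, but ends with "VA with study lenses at Week 1, collected for each eye, on the logMAR scale". None of the three names a worn or a new lens.

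**Schedule.** In SAP Table 10-1, the row for acuity with study lenses (its distance entry begins "Distance (4 m; OD, OS, OU") carries an Old and New label at Visits 3 and 6. It has a plain mark at Visits 2, 4, 5 and 7. Visits 3 and 6 are the Week 1 visits, 7 to 8 days after dispensing.

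**Data rule and summary.** SAP 4 states: "All data obtained in evaluable subjects/eyes will be included in the analysis". SAP 4.3 asks for descriptive statistics and a two-sided 95% confidence interval at Week 1, and then "Similarly, for Dispense and Week 2".

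**Lens supply.** Protocol Table 9-1 has the test lens "Replaced weekly for ~14 days". Table 9-2 has the comparator replaced biweekly and states: "Subjects will receive 1 pair of comparator lenses as per randomization, in parameters as determined during trial".

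**Precision.** SAP 7 takes 92 subjects and an SD of 0.12; the t-based 95% interval, with "coverage probability of 0.85 will extend 0.027 (~1 Snellen letter) from the observed mean".

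**The concern.** Two lens conditions are scheduled at exactly the visits that supply the sole primary endpoint, and the visible text does not choose one. Three analyses then seem possible: the worn lens, the new lens, or both.

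The worn lens gives acuity after 7 to 8 days of wear. The new lens would repeat, for the test product, the unworn state already reported at Dispense. If the comparator really has a single pair, it would also set an unworn test lens beside a worn comparator. Entering both readings as separate rows would count subjects twice and make the interval too narrow. Read literally, the rule that all data obtained are included might seem to invite that. The phrase about each eye in Protocol 12.4.1 adds doubt over whether the value is binocular at all.

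At stake are the reported primary mean and its confidence interval.

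**Working it through.** **1. Reproduce the plan's figure.** Inputs from SAP 7: n = 92, SD = 0.12, two-sided 95%, t-based, probability 0.85 of achieving the half-width.

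- Expected half-width = t(0.975, 91) × SD / √n = 1.9864 × 0.12 / √92 = 0.0249.
- At probability 0.85, multiply by √(χ²(0.85, 91)/91) = 1.074, giving 0.0267. This rounds to the stated 0.027.

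The figure is reached with 92 values, one per subject.

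**2. Try the double-entry reading.** With 184 rows for a product, the same formulas give 0.0175 expected and 0.0184 at probability 0.85. The second is 0.0184/0.0267 = 0.69 of the planned width. It does not match 0.027, so the plan was not sized for pooled Old and New rows.

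**3. What double entry would do.** If Old and New readings have equal means and correlation ρ, the true standard error exceeds the naive one by √(1+ρ). Coverage of the nominal 95% interval is then 2Φ(1.96/√(1+ρ)) − 1. For assumed ρ of 0.5, 0.7 and 0.9 this is 89.0%, 86.7% and 84.5%. The documents give no ρ. These figures describe an analysis that step 2 and the text in step 4 both point away from, so they are not an expected effect.

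**4. Where the data rule sits.** The sentence that seems to admit both readings appears in Protocol 12.5 under the heading on missing data. In both documents it is followed at once by the statement that missing values are not imputed. It says that observed data are kept and nothing is filled in. It does not say how many readings per visit form the endpoint.

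**5. Which single reading fits.**

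| Text | Worn lens | New lens |
|---|---|---|
| Week 1 follow-up, 7 to 8 days after dispensing | fits | not a week of wear |
| 16 hours of wear on the day before each follow-up visit (Protocol 7.1) | conditions this reading | no bearing |
| Dispense summarised separately (SAP 4.3) | adds information | repeats the unworn state |
| Available for both products | yes, however lens supply is read | uncertain for the comparator |

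All four rows favour the worn lens.

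**6. Is the product asymmetry established?** No. Table 9-2 gives the comparator one pair. SAP Table 10-1 marks both dispensing and Old and New at Visits 3 and 6, and in a crossover each of those visits serves both products. The schedule is laid out by period and cannot show product-specific entries. A count of 184 test rows against 92 comparator rows therefore rests on one side of two passages that have to be reconciled. The worn-lens reading exists on either side.

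**7. Each eye or binocular.** The schedule records right eye, left eye and both eyes. SAP 4.1 and Protocol Table 6-1 say binocular without qualification. The phrase in Protocol 12.4.1 is a clerical slip in a sentence that itself says binocular.

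**8. Room for a rule already written.** By the SAP contents list, sections 4.1 to 4.3 run from page 9 to page 13, yet only a few sentences remain visible. In Protocol Table 3-1 the Visit 3 and Visit 6 acuity cells show a mark followed by blacked-out text where the SAP shows the Old and New label. The sponsor evidently treated that detail as confidential in one document, and text that uses it would probably be covered too. Measurement procedures are deferred to the manual of procedures.

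**The case for a change.** The best case for acting is that the primary mean and interval are the study's main effectiveness output and that the primary sentences in SAP 4.1 and 4.3 read as complete, with no gap inside them. A selection rule would cost one sentence in each document. Without it, the reading could in principle be chosen after the data are seen. A shift between worn and new lenses also need not be small against the interval: an assumed difference of 0.01 to 0.04 logMAR is 0.01/0.027 = 37% to 0.04/0.027 = 148% of the planned half-width.

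Part of this stands. The visible wording does not name the reading, a written rule would be tidier, and the single comparator pair has to be reconciled with the schedule marks as an operational matter. The rest carries less weight. The 0.01 to 0.04 range has no source in the documents, so the percentages only rescale an assumption. Choosing a reading after seeing the data matters most where a test or threshold can be won, and here SAP 4.2 sets no hypotheses and the SAP's executive summary says success criteria do not apply. Because of the blacked-out text and the missing manual, it also cannot be said that the plan lacks the rule.

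**Conclusion.** No change to the plan is called for. This is a gap in the visible wording that a competent analyst fills in one way: one binocular reading per subject per product, taken with the lenses worn into the Week 1 visit, with any new-lens reading shown separately. That choice agrees with the time point, the wear instruction, the separate Dispense summary and the precision statement. N = 92 and the half-width of 0.027 do not move, and no test or success decision depends on it.

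The conclusion assumes that Old means the worn lens and New its replacement, which is inferred from the weekly replacement of the test lens because no visible text defines the terms. It also assumes that the blacked-out text and the manual of procedures do not say otherwise; if they name a reading, that settles the question. The size of any Old-to-New difference cannot be judged from the documents.
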